BI IRB# 087-14 Acute and Short-Term Effects of CBD on Cue-Induced Craving in Drug-
Abstinent Heroin-Dependent Humans

NCT # 02539823

Version: March 12, 2017

The purpose of this study is to determine if Cannabidiol (CBD) - one of the natural components of the cannabis plant) is effective in reducing heroin craving. Current therapies available for heroin treatment such as methadone and buprenorphine, do not block heroin craving. Craving is a distressing symptom which is linked to relapse and ultimately the continued cycle of heroin abuse.

45 healthy male and female subjects between the ages of 21 and 65, who are currently abstinent from drug use but who have a recent history (past 3 months) of heroin-dependence will be recruited for the study. There will be 3 groups of 15 subjects. One group will receive a placebo (a solution that does not contain the experimental drug), 15 participants will receive 400 mg of Cannabidiol (CBD), and 15 participants will receive 800 mg of CBD. Dispensation of investigational drug will be randomized and double-blinded.

Participation in this research study will consist of 5 visits in total over a two week period, and will consist of one prescreening session (about 2 hours) and four test sessions. Test sessions 1, 2 and 4 include Cue sessions and will last 3 hours per visit. Test session 3 (no cue session) will last 90 minutes. The investigational drug (CBD) or placebo will be administered during test sessions 1, 2, and 3. There is a 1 week break between test session 3 and 4. There will be no CBD/placebo administration during test session 4.

The prescreening session will consist of:

- | Basic Physical exam
- | Toxicological assessments: urine drug screening including opioid metabolite screening and Breathalyzer. Positive findings will result in exclusion.
- | Urine pregnancy test, blood test (complete blood count, liver function tests, electrolytes, urea, creatinine, glucose), EKG, vital signs (heart rate, blood pressure, weight and height measurement, Body Mass Index calculation), survey of medical history (including tobacco use assessment). MD will determine medical eligibility based on physical exam and lab results.
- | Computerized Structured Clinical Interview for DSM-V (SCID-V) for diagnosing drug dependence. Participants must be positive for current dependence for heroin (within past 3 months), but must not be currently using any drugs (including heroin) besides nicotine.
- | MINI International Neuropsychiatric Interview which is used for the detection of psychiatric conditions. Positive findings for current mood disorders, bipolar disorders and psychotic disorders will result in exclusion.
- | Clinical assessment for withdrawal symptoms - Clinical Opiate Withdrawal Scale (COWS)
- | PI will review pre-screening findings and determine eligibility for enrollment.
- | Computerized attention performance tasks/test

Test Sessions will consist of:

Sessions 1 and 2:

- o Urine drug screening (including opiate metabolite screen), breathalyzer, pregnancy test, questionnaires. Positive findings will result in exclusion.

- CBD/Placebo administration
- Test Session 1 will comprise 2 cue sessions (one 3-minute video of heroin-related imagery plus one 3 minute video of neutral imagery).
- Test Session 2 will comprise 2 cue sessions (one 3-minute video of heroin-related imagery plus 2 minutes of exposure to heroin related paraphernalia; then one 3 minute video of neutral imagery plus 2 minute exposure to neutral paraphernalia)
- Vital signs measurements (blood pressure, heart rate and oxygen saturation) at specific time points
- Questionnaires at specific time points after cues
- 6 saliva samples at specific time points after cues
- SAFETEE to assess for side effects and/or adverse effects
- Debriefing: relaxation exercise to ensure subject is in stable condition (in terms of craving levels) before he/she is discharged
- Take home questionnaire to assess craving at home. To be returned to coordinator at next session.

Session 3: (no cue session)

- Urine drug screening (including opiate metabolite screen), breathalyzer, pregnancy test, questionnaires. Positive findings will result in exclusion.
- Vital signs at specific time points
- Questionnaires at specific time points
- CBD/Placebo administration
- Computer performance tests to assess attention and memory
- SAFETEE to assess for side effects and/or adverse effects
- Take home questionnaire to assess craving at home. To be returned to coordinator at next session.

Session 4 (no CBD/Placebo administered):

- Urine drug screening (including opiate metabolite screen), breathalyzer, tobacco use assessment, pregnancy test, questionnaires.
- 2 Cue sessions (one 3-minute video of heroin-related imagery and one 3 minute video of neutral imagery)
- vital signs measurements (blood pressure, heart rate and oxygen saturation) at specific time points after cues
- 6 saliva samples at specific time points after cues
- SAFETEE to assess for side effects and/or adverse effects
- Debriefing: relaxation exercise to ensure subject is in stable condition (in terms of craving levels) before he/she is discharged

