BI IRB# 087-14 Acute and Short-Term Effects of CBD on Cue-Induced Craving in
Drug- Abstinent Heroin-Dependent Humans

NCT # 02539823

Version: March 12, 2017

Statistical Analysis Plan

A linear mixed-model repeated-measures analysis using the SAS procedure MIXED (SAS Institute, Cary, N.C.) was employed to assess the changes in cue- induced in-clinic VAS-C, VAS-A, and PANAS scores. Changes in the Heroin Craving Questionnaire out-of-clinic craving scale score were assessed using a repeated-measures analysis conducted with the MIXED procedure. At the first stage of all analyses, the distributional characteristics of all continuous explanatory and outcome variables were assessed using skewness and kurtosis indicators. If necessary, transformations were used to normalize a variable. To determine the effectiveness of the randomization procedure for assignment to the drug group, one-way analyses of variance were conducted on the session 1 baseline values of each of the outcome variables as a function of drug group. Nonsignificant drug group baseline differences were taken as indicators of effective randomization. Because a crossover design assumes that there are no carryover effects from one assessment period to the next, this possibility was tested using procedures in the Number Cruncher Statistical System User's Guide II. Once the analyses indicated that carryover effects were absent, the main analyses of the crossover design variables were undertaken.

Difference scores between the precue baseline scores and postcue scores within each session were calculated and used as outcomes in the analytic models. The models themselves were developed sequentially in which time was entered first (because there were multiple sessions and two events within each session for the crossover outcomes; that is, neutral and drug cues). This procedure was followed by entering the variable describing the sequence in which the drug and neutral cues were given, the drug group variable, and the cue indicator (neutral or drug cue). A single first-order interaction term (drug group by cue) was entered last because it was hypothesized that the cues would be responded to differentially depending on the drug group to which the research participant was assigned. Any significant mean differences for the main effect analyses or interaction terms were followed up by Tukey-adjusted post hoc mean comparisons.

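### Does excluding people after a positive screen at session 2 or 3 require the SAP to name an analysis set?

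*Protocol*

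**What the plan says.** The protocol's opening description gives three groups of 15 and says "The investigational drug (CBD) or placebo will be administered during test sessions 1, 2, and 3". Cue sessions take place at sessions 1, 2 and 4. The lists for sessions 1 and 2 and for session 3 both carry the line "Urine drug screening (including opiate metabolite screen), breathalyzer, pregnancy test, questionnaires. Positive findings will result in exclusion". The session 4 list has the corresponding line, "Urine drug screening (including opiate metabolite screen), breathalyzer, tobacco use assessment, pregnancy test, questionnaires", with no consequence attached. Sessions 1 to 3 also include "Take home questionnaire to assess craving at home. To be returned to coordinator at next session".

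The SAP fits a linear mixed model in SAS MIXED to differences between pre-cue and post-cue scores within each session. Of the model terms it says "A single first-order interaction term (drug group by cue) was entered last", because that is the hypothesised effect. For the take-home outcome it says "Changes in the Heroin Craving Questionnaire out-of-clinic craving scale score were assessed using a repeated-measures analysis conducted with the MIXED procedure". It defines no analysis set and gives no rule for participants excluded after dosing.

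**The concern.** At prescreening, exclusion means that the person never enters the trial. Used again after dosing, the same word could mean no further visits, or removal from the trial's data. The second meaning would delete randomised participants because of something that happened after randomisation.

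The reason for removal may also be tied to the outcome, since the protocol says "Craving is a distressing symptom which is linked to relapse". If CBD lowers craving and craving leads to positive screens, deletion would remove more high-craving people from placebo than from CBD and shrink the difference between arms. Precision would fall in a trial of 15 per arm even if losses were equal. An unwritten rule can also be settled after results are seen. Session 4 leaves a similar question, because the screen is repeated with no stated effect on the analysis.

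**Working it through.** **Inputs from the documents.** 3 × 15 = 45 participants; cue sessions 1, 2 and 4 with two cues each, so 6 cue scores per person; take-home questionnaires after sessions 1, 2 and 3. The plan gives no alpha, power, effect, SD or exclusion rate, so there is no power figure to reproduce.

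**Assumed inputs.** Unit SD; correlation 0.5 between any two scores of one person; effect 0.80 SD confined to the drug cue; 1 or 3 exclusions per arm, unrelated to craving and not replaced.

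**Step 1: data at stake.** By the listed order, someone excluded at session 2 has given 2 of 6 cue scores and 1 of 3 questionnaires; at session 3, 4 of 6 and 2 of 3. With 3 per arm (9 people), deletion discards 9 × 2 = 18 to 9 × 4 = 36 of 45 × 6 = 270 cue scores (7–13%), and 9 to 18 of 135 questionnaires.

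**Step 2: what the plan does with them.** Each outcome is formed within one session, so a completed session gives usable rows whatever happens later. MIXED does not need complete records. Keeping the rows is the default; deleting them needs a separate decision that neither document makes.

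**Step 3: standard errors, placebo against one CBD arm.**

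- Group by cue: one session's drug-minus-neutral difference has variance 2(1 − 0.5) = 1, and differences from different sessions are uncorrelated. With m person-sessions per arm, SE = √(2/m). Full data: m = 45, SE 0.211. Three excluded and deleted: m = 36, SE 0.236. Three kept: m = 36 + 3 = 39 (session 2), SE 0.226, or m = 36 + 6 = 42 (session 3), SE 0.218.
- Drug-cue contrast: a person's mean over three sessions has variance (1 + 2 × 0.5)/3 = 0.667, so SE = √(2 × 0.667/n). For n = 15, 14 and 12 this gives 0.298, 0.309 and 0.333. The kept-data values come from the same model by generalised least squares.

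Power = Φ(0.80/SE − c). For group by cue, c = 1.96 (one contrast, two-sided 0.05, unadjusted). For the drug-cue contrast, c is the Tukey value at 42 df: 2.43 for 3 means or 2.99 for 6 cells.

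| Excluded per arm | Handling | Group-by-cue SE | Power | Drug-cue SE | Power, 3 means | Power, 6 cells |
|---|---|---|---|---|---|---|
| 0 | full | 0.211 | 97% | 0.298 | 60% | 38% |
| 1 | kept | 0.213–0.216 | 96% | 0.299–0.301 | 59–60% | 37–38% |
| 1 | deleted | 0.218 | 96% | 0.309 | 56% | 35% |
| 3 | kept | 0.218–0.226 | 94–96% | 0.301–0.307 | 57–59% | 35–37% |
| 3 | deleted | 0.236 | 92% | 0.333 | 49% | 28% |

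For group by cue, keeping the data recovers (0.236 − 0.226)/(0.236 − 0.211), about 37% of the SE loss on unrounded values, when exclusions fall at session 2, and about 70% when they fall at session 3. The rest is lost because later visits do not take place, which no analysis rule can restore.

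**Step 4: dilution if exclusion follows craving.** This was simulated with 400,000 per arm, 7–20% of placebo excluded, and correlation 0.3–0.5 between the tendency to be excluded and the missed drug-cue score. The drug-cue contrast shrinks by 0.3–2.5% if data are kept and 1.1–7.6% if deleted. Group by cue shrinks by 0.3–1.8% under either handling. If CBD has no effect and exclusion depends on craving in the same way in each arm, bias is within 0.003 SD.

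**The case for a change.** The strongest case for a change is that a software default protects only rows left in the dataset. Whether an excluded person's rows are left there is decided before the model runs, and that decision is unwritten. A few SAP sentences and a table of exclusions by arm, session and reason would settle it at almost no cost.

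Deletion can also cost more than the table shows. In a second simulation the drug-minus-neutral difference was itself correlated 0.5 across sessions, and exclusion rose with the previous session's response (log-odds slope 1 per SD). With about 19% excluded, deletion gave a mean estimate of 0.743 against 0.809 with full data, and power of 60% against 77% (unadjusted).

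It stands that the text is silent and that deletion would be a poor choice. But in that same simulation, keeping the data gave 0.807 and power of 74%, so the handling that the plan produces by default performs well even there. The wording also favours that reading. The rule sits in visit lists, beside dosing and cue procedures, and never mentions analysis. It is absent at session 4, the last visit, where no dose or later visit remains. A rule about removing data would be needed there as much as anywhere.

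High exclusion rates have no support in the documents either. Five visits fit in two weeks and "There is a 1 week break between test session 3 and 4", so prescreening to session 3 spans about one week, in people who screened negative at entry. The rule also covers pregnancy and breathalyzer results, so not every exclusion would track craving.

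**Conclusion.** The concern does not call for a change. It is correct that the session 2 and 3 screens reach people already dosed and that the SAP names no analysis set. This is a gap that an analyst fills sensibly by running the stated model on the data collected, and a new sentence would only write down what the plan already does. A positive screen at session 4 has no stated consequence, and on the same reading those scores stay in.

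Under the deletion reading, the loss on group by cue is about 2 to 3 power points with 3 exclusions per arm and under 1 point with 1 per arm. On the drug-cue contrast it is about 8 to 10 points over three means with 3 per arm (about 7 to 9 over six cells), and about 3 points with 1 per arm. These figures rest on assumed correlation, effect and exclusion counts, and on excluded people not being replaced, which the documents do not address. If groups were filled to 15 completers, deletion would still discard data but the standard error would not rise to 0.333. A report that states how many people were excluded, by arm and reason, would let a reader confirm which handling was used.

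### No SAFETEE is listed before the first dose, so side effects lack a same-instrument baseline, and effects arising after discharge are next elicited only after the following dose

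*Protocol*

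**What the plan says.** The protocol's overview sets three dosing occasions and one undosed visit: "The investigational drug (CBD) or placebo will be administered during test sessions 1, 2, and 3" and "There will be no CBD/placebo administration during test session 4". On visit length it says "Test sessions 1, 2 and 4 include Cue sessions and will last 3 hours per visit", and "Test session 3 (no cue session) will last 90 minutes". On spacing it gives "5 visits in total over a two week period" and "There is a 1 week break between test session 3 and 4"; the intervals from Session 1 to 2 and from Session 2 to 3 are not given.

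Side effects are assessed by "SAFETEE to assess for side effects and/or adverse effects". This item appears in the shared list for Sessions 1 and 2, in the Session 3 list and in the Session 4 list. In the three dosed sessions it comes after study drug. The prescreening list does not contain it. Nor does the arrival item of the dosed sessions, which holds toxicology, breathalyzer, pregnancy test and questionnaires that are not named.

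Withdrawal is scored once, at prescreening: "Clinical assessment for withdrawal symptoms - Clinical Opiate Withdrawal Scale (COWS"). The form that participants take home after Sessions 1, 2 and 3 covers craving. The SAP models craving, anxiety and affect scores and mentions neither SAFETEE nor adverse events.

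**The concern.** Participants have been heroin-dependent within the past 3 months and are now abstinent. Residual complaints before any study drug are plausible in such people. If the first SAFETEE follows the first dose, a complaint that was already there is recorded in the same way as one that the drug caused, and nothing on the same instrument tells them apart within a person.

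The second issue is timing between visits. A symptom that starts at home after Session 1 or 2 has no listed form to catch it until the next SAFETEE, which is listed after the next dose. The answer may then combine late effects of one dose with early effects of the next. What is at stake is the attribution of side effects to drug and to dose, in a study that compares 400 mg and 800 mg of CBD with placebo.

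**Working it through.** The plan states no figure on this point, so there is none to reproduce. The check sets the session lists side by side.

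**Step 1. Order of dose and SAFETEE, reading each list from top to bottom.**

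| Visit | Study drug | SAFETEE | SAFETEE listed before that visit's dose |
|---|---|---|---|
| Prescreening | no | no | n/a |
| Session 1 | dose 1 | yes, below dose | no |
| Session 2 | dose 2 | yes, below dose | no |
| Session 3 | dose 3 | yes, below dose | no |
| Session 4 | none | yes | n/a |

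SAFETEE administrations listed: 4. Listed before dose 1: 0.

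**Step 2. What the same-visit SAFETEE covers.** The sequence is dose 1, SAFETEE, dose 2, SAFETEE, dose 3, SAFETEE, then an undosed SAFETEE. Each of doses 1 and 2 is therefore followed by one structured elicitation before the next dose. Its reach is bounded by visit length: at most 3 hours after doses 1 and 2, and at most 1.5 hours after dose 3.

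**Step 3. What it does not cover.** The gap runs from discharge to the next arrival.
- After doses 1 and 2, the next SAFETEE is listed after another dose, so effects can mix. That is 2 of the 3 between-visit intervals.
- After dose 3, the next SAFETEE is at Session 4, undosed and about a week later. No mixing with a later dose arises there, but the recall window is not stated.

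The length of the first two gaps cannot be computed, because the intervals are not given. As an assumption, if visits start 24 hours apart the uncovered time is 24 − 3 = 21 hours; if 72 hours apart, 72 − 3 = 69 hours. The overall limit is two weeks less the one-week break, so about 7 days for prescreening through Session 3.

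**Step 4. What the placebo arm can and cannot supply.** Let a symptom be present before dosing with probability p in every participant, independently, with no drug effect. The documents give no p, so 20%, 30% and 50% are assumptions. The expected count per arm is 15p. For two arms, X and Y ~ Binomial(15, p), and the chance of a gap of 3 or more participants is P(|X − Y| ≥ 3).

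| p | Expected per arm, 15p | P(gap ≥ 3), two given arms | P(largest gap ≥ 3), three arms |
|---|---|---|---|
| 0.20 | 3.0 | 0.249 | 0.48 |
| 0.30 | 4.5 | 0.318 | 0.58 |
| 0.50 | 7.5 | 0.362 | 0.63 |

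This is ordinary chance imbalance under randomisation, not bias. A gap of 3 would not by itself be taken as a drug effect: the most extreme case, 0 of 15 against 3 of 15, gives a two-sided Fisher p of 0.22. The table shows only how much background noise a within-person baseline would help to identify.

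**The case against.** **The lists are not declared to be timetables.** This is true. Session 3 places vital signs and questionnaires with several time points above the dose, whereas Sessions 1 and 2 place such items below it. Still, the Sessions 1 and 2 list runs from arrival checks through dosing to debriefing and take-home material, which reads as visit order. If it is not, SAFETEE timing is simply unspecified and still needs to be stated.

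**There are other pre-dose references.** Prescreening has history, physical examination, bloods, EKG, vital signs and COWS, and a randomised, double-blind placebo arm runs alongside. This stands. A reader might infer that the trial has no pre-dose reference at all, or that drug effects cannot be separated from existing symptoms; neither follows. What is missing is a baseline on the same instrument. The unnamed arrival questionnaires might contain symptom items, but nothing in the documents says so.

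**Earlier doses are checked.** A reader might also infer that doses 2 and 3 are given before any systematic questioning about the previous dose. The lists contradict this: the SAFETEE in Sessions 1 and 2 follows that visit's dose and is listed before debriefing and discharge. Only effects arising after discharge are left over.

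**No planned estimate depends on it.** This also stands. The stated purpose is craving, and the SAP plans no SAFETEE comparison.

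**COWS should be repeated.** A reader might ask for this because withdrawal is scored once. The documents set no aim of measuring change in withdrawal, so a single score is not a defect against their own objectives.

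**Conclusion.** The point holds in a limited form. Taking list order as visit order, 0 of 4 SAFETEE administrations precede the first dose, so an individual's symptom cannot be classed on that instrument as new, worse or pre-existing. After doses 1 and 2, effects that arise at home are next elicited by a form that follows another dose, and how long that gap lasts cannot be determined from the documents. The validity of the between-arm comparison is not in question, and the craving results are unaffected. The loss is in attributing side effects to drug and to dose, with 15 per arm to rely on. The conclusion rests on the lists being in visit order and on the unnamed arrival questionnaires not already containing a symptom baseline.

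**What to change.** - Administer the existing SAFETEE on arrival, before study drug, at Sessions 1, 2 and 3. At Sessions 2 and 3 its recall window should be the time since the last visit.
- Keep the post-dose SAFETEE in each dosed session, and state its clock time relative to dosing and its recall window. State the recall window at Session 4 as well.
- Add to the SAP that treatment-emergent symptoms are those new or worse than the Session 1 pre-dose form, tabulated by arm.

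The cost is protocol and SAP wording and a few extra minutes at three visits, with a form already in use. The downside is slightly longer dosed visits. This is a change to measurement and reporting only; no dosing or dispensing rule is proposed.

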BI IRB# 087-14 Acute and Short-Term Effects of CBD on Cue-Induced Craving in
Drug- Abstinent Heroin-Dependent Humans

NCT # 02539823

Version: March 12, 2017

Statistical Analysis Plan

A linear mixed-model repeated-measures analysis using the SAS procedure MIXED (SAS Institute, Cary, N.C.) was employed to assess the changes in cue- induced in-clinic VAS-C, VAS-A, and PANAS scores. Changes in the Heroin Craving Questionnaire out-of-clinic craving scale score were assessed using a repeated-measures analysis conducted with the MIXED procedure. At the first stage of all analyses, the distributional characteristics of all continuous explanatory and outcome variables were assessed using skewness and kurtosis indicators. If necessary, transformations were used to normalize a variable. To determine the effectiveness of the randomization procedure for assignment to the drug group, one-way analyses of variance were conducted on the session 1 baseline values of each of the outcome variables as a function of drug group. Nonsignificant drug group baseline differences were taken as indicators of effective randomization. Because a crossover design assumes that there are no carryover effects from one assessment period to the next, this possibility was tested using procedures in the Number Cruncher Statistical System User's Guide II. Once the analyses indicated that carryover effects were absent, the main analyses of the crossover design variables were undertaken.

Difference scores between the precue baseline scores and postcue scores within each session were calculated and used as outcomes in the analytic models. The models themselves were developed sequentially in which time was entered first (because there were multiple sessions and two events within each session for the crossover outcomes; that is, neutral and drug cues). This procedure was followed by entering the variable describing the sequence in which the drug and neutral cues were given, the drug group variable, and the cue indicator (neutral or drug cue). A single first-order interaction term (drug group by cue) was entered last because it was hypothesized that the cues would be responded to differentially depending on the drug group to which the research participant was assigned. Any significant mean differences for the main effect analyses or interaction terms were followed up by Tukey-adjusted post hoc mean comparisons.

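### The in-clinic model has no drug-group-by-session term, so it gives one session-averaged CBD effect and cannot separate dosed cue sessions 1 and 2 from undosed session 4

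*SAP*

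**What the plan says.** The protocol's visit description fixes the cue sessions: "Test sessions 1, 2 and 4 include Cue sessions and will last 3 hours per visit". CBD or placebo is given at sessions 1, 2 and 3, and for the last visit the protocol says: "There is a 1 week break between test session 3 and 4. There will be no CBD/placebo administration during test session 4". The Session 4 list confirms that cue testing is repeated there: "2 Cue sessions (one 3-minute video of heroin-related imagery and one 3 minute video of neutral imagery". The cue data therefore come from two dosed sessions and one undosed session.

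The SAP's second paragraph builds the in-clinic model on precue-to-postcue difference scores. Time goes in first, "because there were multiple sessions and two events within each session for the crossover outcomes". Cue sequence, drug group and cue follow. Then: "A single first-order interaction term (drug group by cue) was entered last". Significant main effects or interaction terms are "followed up by Tukey-adjusted post hoc mean comparisons". The SAP does not list the sessions that enter the model, and it gives no separate analysis of session 4.

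The out-of-clinic outcome is handled apart: "Changes in the Heroin Craving Questionnaire out-of-clinic craving scale score were assessed using a repeated-measures analysis". The terms of that model are not given, so this point does not extend to it.

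**The concern.** The title promises "Acute and Short-Term Effects of CBD on Cue-Induced Craving". Neither document defines the two kinds of effect. On any reading that ties them to different cue sessions, the planned in-clinic analysis returns only their average.

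The model contains no drug group by session, cue by session, or drug group by cue by session term. The Tukey comparisons apply only to terms in the model, and a comparison on time contrasts sessions averaged over drug groups. Neither yields a session-specific CBD contrast.

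Three things are at stake. A significant pooled result could be read as a lasting effect when there is none. An effect that has gone by session 4 is diluted. Any session contrast chosen after the data are seen would be unplanned.

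**Working it through.** The documents give no SD, correlation, effect size, alpha or power, so there is no stated figure to reproduce. The first two steps below are algebra; the power and precision figures in the later steps are illustrative.

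**Inputs from the documents.** 45 participants in three groups of 15 (protocol, opening description); cue sessions 1, 2 and 4, each with a drug and a neutral cue; model terms as in the SAP's second paragraph.

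**1. What the model can express.** Let D be a participant's drug-cue response minus neutral-cue response in one session. Session and sequence main effects cancel in D. What is left is the cue effect plus the group-by-cue effect, and neither carries a session index. The CBD-minus-placebo difference in D is therefore one number per dose, the same at sessions 1, 2 and 4.

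**2. What it estimates.** With complete balanced data the group-by-cue coefficient is (δ1 + δ2 + δ4)/3, where δ is the true effect in each session. For (d, d, 0) this is 2d/3 = 0.67d. Fitting the SAP's terms to noise-free data (45 × 3 × 2 records) gave:

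| True effect at sessions 1, 2, 4 | Size of coefficient |
|---|---|
| 1.2, 0, 0 | 0.40 |
| 0.6, 0.6, 0 | 0.40 |
| 0.4, 0.4, 0.4 | 0.40 |
| 0, 0.6, 0.6 | 0.40 |
| 0, 0, 1.2 | 0.40 |

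The equal weighting also held with time coded as six session-by-event levels, and with a compound-symmetric covariance for three-level time. Missing sessions or an unstructured covariance change the weights, but the result is still a single average. Adding the two-way session terms and the three-way term (9 fixed-effect columns become 19, full rank) recovered each session's effect.

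**3. Illustrative power.** Assumed: SD of D equal to 1, between-session correlation ρ = 0.5, effect of 1 SD, one dose against placebo, two-sided 0.05, 45 − 3 = 42 df.

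- Variance of a participant's mean D: three sessions (1 + 2ρ)/3 = 0.667; two sessions (1 + ρ)/2 = 0.75; one session 1.
- SE = √(variance × 2/15): 0.298, 0.316 and 0.365.
- Power is from the noncentral t with noncentrality = expected estimate / SE. For (1, 1, 0): pooled 0.667/0.298 = 2.24; sessions 1–2 1/0.316 = 3.16.
- Critical value 2.018 unadjusted; 2.429 for a three-group Tukey comparison (in brackets).

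| True pattern | Pooled | Sessions 1–2 | Session 1 |
|---|---|---|---|
| Gone by session 4 (1, 1, 0) | 58.9% (43.1%) | 87.1% (76.5%) | – |
| Persistent (1, 1, 1) | 90.6% (81.8%) | 87.1% (76.5%) | – |
| Session 1 only (1, 0, 0) | 19.4% (10.5%) | 33.9% (21.0%) | 76.3% (62.3%) |

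A simulation of 20,000 trials gave 59.1%, 90.4% and 19.4% for the pooled column. For ρ from 0.3 to 0.7, the first row (pooled against sessions 1–2, unadjusted) runs from 69% against 91% to 51% against 83%. The second runs from 96% against 91% to 85% against 83%.

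**4. When pooling is better.** If session 4 keeps a fraction f of the effect, the pooled estimate has expectation (2 + f)d/3. Equating noncentralities gives f = 3√(0.667/0.75) − 2 = 0.83 (0.72 at ρ = 0.3, 0.91 at ρ = 0.7). Pooling is more powerful only above that fraction.

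**5. Precision of the alternative.** The 95% half-width is 2.018 × SE: 0.60 SD pooled, 0.64 for sessions 1–2, 0.74 for one session. The difference between the CBD effect at sessions 1–2 and at session 4 has per-participant variance (1 + ρ)/2 + 1 − 2ρ = 0.75. The difference detectable with 80% power is about 0.91 SD (1.07 at ρ = 0.3, 0.70 at ρ = 0.7).

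**The case against.** The strongest reply is that the planned test answers the hypothesis the SAP states, namely that response to the cues depends on drug group. A session-averaged effect is a legitimate target for that hypothesis, and the contrary reading leans on two undefined words in the title. This stands in part: the group-by-cue test is valid as a test of an average. But the trial schedules a cue visit a week after the last dose, and no planned in-clinic contrast isolates it.

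Second, the SAP never says that session 4 is in the model. That is true. If session 4 is out, the 0.67d dilution and the 59% against 87% comparison fall away. What remains is an undosed cue session with no planned in-clinic analysis, and sessions 1 and 2 still averaged although session 2 adds paraphernalia exposure.

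Third, the power figures depend on assumptions. At 0.5 SD and correlation 0.5, power for an effect gone by session 4 is poor throughout: 19% pooled, 34% for sessions 1–2, 27% for session 1 alone. At correlation 0 the break-even falls to 45%. The SAP's Tukey procedure could also mean six cell means rather than three groups. These points limit the illustration but leave the algebra untouched.

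Fourth, a contrast of sessions 1–2 with session 4 also reflects cue type and a third dose. That is a reason to report each session against concurrent placebo and to judge persistence from session 4 itself.

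**Conclusion.** The concern holds. The missing session interactions follow directly from the SAP's text, and the averaging is algebra that needs no assumed SD or correlation; equal weights need complete data and an exchangeable covariance. The planned in-clinic analysis cannot show whether a CBD effect is confined to dosed sessions, persists a week later or appears only then.

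Pooling of session 4 is an inference, but neither reading of the SAP gives a session-specific contrast. On the illustrative figures at correlation 0.5, pooling loses about 28 percentage points of power (87.1 − 58.9) if the effect has gone by session 4, and gains about 3.5 (90.6 − 87.1) if it persists. The limit lies in the planned analysis: the trial collects data by session against concurrent placebo, which is enough to estimate the session effects.

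**What to change.** - State explicitly which sessions enter the in-clinic model, and whether session 4 is one of them.
- Treat session as categorical and add drug group by session, cue by session, and drug group by cue by session.
- Prespecify each dose against placebo on the drug-minus-neutral response, with confidence intervals, for sessions 1 and 2 (individually and averaged) and separately for session 4. Name the primary contrast and the handling of multiplicity.
- Judge persistence from the session 4 estimate and its interval. With about 0.91 SD detectable at 80% power, a non-significant three-way term would say little.
- If the session-averaged effect is kept, label it as an average over dosed and undosed sessions.

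The change is to SAP wording, model terms and contrasts; it needs no new participants or visits. The costs are wider intervals (0.74 SD for one session against 0.60 pooled), slightly less power if the effect persists, and more contrasts to control. Bonferroni over all eight (two doses by four contrasts) would bring power at 1 SD and correlation 0.5 down to about 61% for sessions 1–2 and 45% for one session, so a single primary contrast should be named.
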